Part A: International guidelines recommend TB screening for prisoners, but they do not offer any specific guidance on how to most effectively screen them, especially given restricted budgets (especially for prisoners) in resource-constrained settings. We hypothesize that HIV+ prisoners should be prioritized for screening since TB incidence is minimally 10% per year (higher in Malaysian prisoners based on our previous pilot data) vs 10% lifetime in HIV-s. We also hypothesize that a number of screening methods are available, but will have differential impact on prevalence, incidence and transmission to others (including to prison staff). Precision in the estimates will be used for calculations in Aim 2. All analyses will conform to the STARD guidelines for diagnostic accuracy reporting (www.stard-statement.org/). Using standard measures for establishing prevalence and incidence of active and LTBI, frequencies will be calculated for categorical variables and median with standard deviation (SD) or interquartile range (IQR) for continuous variables depending on whether the data were normally distributed or not, respectively. Chi square and Student t-tests will compare between Xpert-negative/culture-positive and Xpert-positive/culture-positive groups. Sensitivity, specificity, positive (PPV) and negative (NPV) predictive values of the Xpert and their respective 95% confidence intervals (95% CI) will be calculated compared to the results of active TB defined using the gold-standard MGIT 960 liquid culture.^{39,40} For variables identified as being strongly collinear with each other (age, duration of drug use and duration of cigarette smoking), final models for diagnostic accuracy will be based on the most optimal goodness-of-fit using the Akaike Information Criterion (AIC). When combining results from multiple screening tests (e.g., symptoms + CXR or symptoms + Gene Xpert), we will examine multiple thresholds using pair measures, or Receiver Operator Curves (ROC), where sensitivity and specificity (or even predictive values) differ across thresholds. Such methods provide better discriminative power when adjusting the threshold (e.g., varying levels of TB symptoms).⁴¹ Using estimates of LTBI of 84% and active TB 10-15% with a 95% CI and SE=0.025 among a cross-sectional population of ~4800 HIV+ prisoners, a sample size of 214 HIV+ and 214 HIV- participants would be needed. Thus, a sample of 250 HIV- and 250 HIV+ prisoners (N=500) should be more than adequate. No loss to follow-up is expected because sentenced prisoners must serve at least 90 days and can easily complete screening procedures.

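### Part A compares Xpert-negative with Xpert-positive culture-confirmed cases by chi-square and Student t-tests only, with no alternative for skewed variables or sparse tables

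*Combined protocol and SAP*

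**What the plan says.** Everything relevant is in Section V, item 12 (Statistical Considerations), Part A of the combined protocol and SAP.

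- **Summaries.** The measure of spread is SD or IQR "for continuous variables depending on whether the data were normally distributed or not".
- **Tests.** The next sentence reads "Chi square and Student t-tests will compare between Xpert-negative/culture-positive and Xpert-positive/culture-positive groups". No exact test, rank test or transformation is named for Part A.
- **Size.** The calculation starts "Using estimates of LTBI of 84% and active TB 10-15% with a 95% CI and SE=0.025", "among a cross-sectional population of ~4800 HIV+ prisoners". It concludes that "a sample size of 214 HIV+ and 214 HIV- participants would be needed" and that "a sample of 250 HIV- and 250 HIV+ prisoners (N=500) should be more than adequate".

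The plan gives no Xpert sensitivity and no expected number of Xpert-negative cases. It claims no power for this comparison. The only sensitivity quoted, 67% in Section V, item 3, is for the urinary TB-LAM test.

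**The concern.** The normality condition governs how a variable is described but not how it is tested. A variable that the plan itself judges non-normal would be shown with an IQR and then tested with Student's t on the raw scale. Because the plan names the tests, this is a stated method that can be improved and not simply an omitted detail.

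The comparison divides the culture-positive cases, who are a small fraction of the sample, into two unequal parts. That is where the large-sample approximation behind chi-square is weakest, and where a raw-scale t-test on skewed data behaves differently according to which group has the higher values. At stake is the plan's direct look at which TB cases Xpert misses.

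**Working it through.** **1. The plan's own figure.** Taking 0.025 as the standard error of a prevalence, n = p(1 − p)/SE². With p = 0.84 this is 0.84 × 0.16 / 0.025² = 215.04, against the stated 214. The figure is reproduced to within rounding. Part A is therefore sized on the precision of a prevalence, not on this comparison.

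**2. Culture-positive cases.** Assume every active case is culture-positive.
- One HIV group: 250 × 0.10 = 25 to 250 × 0.15 = 37.5.
- All participants, if the rate also held in HIV-negative prisoners: 500 × 0.10 = 50 to 500 × 0.15 = 75.

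**3. Xpert-negative cases** = cases × (1 − sensitivity), with sensitivity **assumed** to be 60-90%.
- One HIV group: 25 × 0.10 = 2.5 to 37.5 × 0.40 = 15.
- All participants: 50 × 0.10 = 5 to 75 × 0.40 = 30.

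**4. Sparse cells.** The smallest expected count is n₁ × min(s, N − s)/N, where n₁ is the smaller group, s the number with the characteristic and N the total. It cannot exceed n₁/2, so with fewer than 10 Xpert-negatives it is always below 5. At 10 v 40 it is below 5 in at least 89% of samples for characteristics of 5-50%. At 15 v 60 the share is 99.5% for a 20% characteristic, 70% for 30% and 0.2% for 50%.

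**5. Type I error of uncorrected chi-square** at nominal 5%, by exact enumeration of two binomials:

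| Xpert-neg v Xpert-pos | 5% characteristic | 10% | 20% | 30% | 50% |
|---|---|---|---|---|---|
| 5 v 20 | 9.0% | 7.6% | 4.7% | 4.5% | 5.6% |
| 8 v 30 | 9.3% | 6.2% | 4.2% | 5.0% | 4.6% |
| 10 v 40 | 7.8% | 4.5% | 4.3% | 4.8% | 5.5% |
| 15 v 60 | 6.0% | 3.4% | 5.0% | 4.8% | 5.6% |

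At 8 v 30, Fisher mid-P gives 1.6-4.5% over the same range, and the Yates-corrected chi-square gives 0.3-1.9%.

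**6. Power for a right-skewed marker**, by simulation. Data are log-normal with a shift of 0.9 SD on the log scale, two-sided 5%. The degree of skew and the size of the shift are **assumptions**. At 8 v 30:

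| Log SD | Raw t, Xpert-neg lower | Raw t, Xpert-neg higher | Wilcoxon, either way | Log-scale t, either way |
|---|---|---|---|---|
| 0.4 | 48% | 62% | about 55% | about 60% |
| 0.6 | 40% | 61% | about 55% | about 60% |
| 1.0 | 17% | about 59% | about 55% | about 60% |

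At 15 v 60 with log SD 1.0 and the Xpert-negative group lower, the raw t-test has 47% against 85% for Wilcoxon. At 25 v 25 with log SD 1.0 it has about 70% against 85% in either direction. That balanced split corresponds to a sensitivity of 50% with 50 cases, which is outside the range assumed in step 3, so it is illustrative only.

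**The case against.** The case against making much of this is substantial, and most of it stands.

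- **Direction.** At 8 v 30 the raw t-test beats Wilcoxon by a few points when the Xpert-negative group is higher. Nothing in the documents says which way CD4 count, liver enzymes or duration of drug use would differ. A reader might infer that the planned t-test loses power in general. It does so under strong skew when the smaller group is lower, or when the groups are balanced. What remains is that its power swings from about 17% to 59% for the same log-scale effect, while the log-scale t-test is steady.
- **Type I error.** A reader might infer that the chi-square p-values are broadly wrong. At the 5% level they are mostly near nominal, and the inflation is confined to rare characteristics in small groups. The plan does not say whether a continuity correction applies; with one, the test at 8 v 30 is conservative.
- **Power of the chi-square.** Replacing it with mid-P buys error control, not power. The main limit is the number of cases: for 60% v 30%, power is 0.28 at 5 v 45 and 0.58 at 15 v 60.
- **Wording of the plan.** It allows for non-normal data but does not say that it expects them. It also does not say that the comparison is run within HIV groups.
- **Consequence.** This is a secondary descriptive comparison, and exact and rank tests are routine fallbacks.

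None of this removes the mismatch between the two adjacent sentences.

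**Conclusion.** The point holds as a minor one. The plan applies its normality condition to summaries only, and names two tests that fit poorly with skewed variables and sparse tables. For continuous variables the cost ranges from nothing to a large loss of power, depending on skew and direction (17% against about 55-60% in the worst case shown). For categorical variables the cost is a type I error of about 8-9% for a 5% characteristic at 5 v 20, 8 v 30 and 10 v 40, and little otherwise.

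These sizes rest on an assumed Xpert sensitivity of 60-90%, on 10-15% active TB (which the plan ties to HIV-positive prisoners), and on log-normal markers. It would go too far to say that the Xpert-negative group will certainly be very small. The assumed range runs from about 3 in one HIV group to about 30 overall, and the documents give no sensitivity that would narrow it. It would also go too far to say that Part A's main results are at risk: sensitivity, specificity, PPV and NPV do not depend on these tests.

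**What to change.** Replace the sentence that names the tests with one providing that:

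- continuous variables that fail the plan's own normality check are compared by a t-test on the log scale or a Wilcoxon rank-sum test, with Student's t kept for the rest;
- categorical variables are compared by Fisher's exact test with mid-P whenever an expected count is below 5, and by chi-square otherwise;
- each difference is reported with a 95% CI, and the comparison is labelled exploratory.

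Add the expected number of Xpert-negative/culture-positive cases and the sensitivity assumed for it, and say whether the HIV groups are pooled.

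The cost is a sentence or two of text, with no change to data collection, staff or sample size. There are two small downsides. Mid-P is somewhat conservative for rare characteristics (1.6% at 8 v 30 for a 5% characteristic). Wilcoxon gives up a few points of power to the raw t-test when the smaller group is shifted upward; the log-scale t-test largely avoids this where a log transformation is reasonable.

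### Part A explores cut-offs and test combinations in one small sample with no selection rule and no internal validation, so a best strategy named from it will tend to look too sensitive

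*Combined protocol and SAP*

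**What the plan says.** Section V.12, Part A, plans three kinds of accuracy analysis in one sample of 500 (250 HIV+ and 250 HIV-).

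- **Xpert alone** against MGIT 960 liquid culture, with intervals: "predictive values of the Xpert and their respective 95% confidence intervals (95% CI) will be calculated". No data-chosen cut-off is involved.
- **A model choice by AIC**, limited at the start of its sentence: "For variables identified as being strongly collinear with each other (age, duration of drug use and duration of cigarette smoking"), and then "final models for diagnostic accuracy will be based on the most optimal goodness-of-fit using the Akaike Information Criterion (AIC").
- **Combined tests**: "When combining results from multiple screening tests (e.g., symptoms + CXR or symptoms + Gene Xpert"), followed by "we will examine multiple thresholds using pair measures, or Receiver Operator Curves (ROC), where sensitivity and specificity (or even predictive values) differ across thresholds". The reason given is "Such methods provide better discriminative power when adjusting the threshold (e.g., varying levels of TB symptoms").

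The combinations are examples, not a closed list. The section states no cut-off, number of thresholds or rule for choosing among them, and no split sample, cross-validation, bootstrap or optimism correction. It commits to STARD, which governs reporting.

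On use of the results, Section IX gives the benefit of Part A as finding the best TB screening strategy for prisoners. Section V.12 adds "Precision in the estimates will be used for calculations in Aim 2", and Section V.1 says the Aim 2 modelling draws on Aim 1 data together with public data.

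**The concern.** When a cut-off or a combination is picked because it performed best in a sample, part of that performance is chance. Accuracy recomputed on the same people keeps the chance part. The effect falls mainly on sensitivity, because culture-positive cases are few.

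Two things are at stake. First, the comparison within Part A is uneven: Xpert alone has nothing tuned, whereas a combination tuned on the data carries a built-in advantage. Second, Aim 2 compares the cost-effectiveness of screening strategies. Any overstated sensitivity used there would favour the tuned strategy again.

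**Working it through.** **Inputs from Section V.12.** LTBI 84%, active TB 10-15%, SE 0.025, 250 participants per HIV stratum.

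**Reproducing the plan's sample size.** n = p(1-p)/SE² = 0.84 × 0.16 / 0.025² = 215, against 214 stated. Active TB does not give it: p = 0.15 gives 204 and p = 0.10 gives 144. The sample was therefore sized for LTBI prevalence, not for the sensitivity of a screening rule.

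**Cases available.** 250 × 0.10 = 25 and 250 × 0.15 = 37.5, so 25-38 among HIV+ participants. Applying the same rates to all 500 gives 50-75. That is a ceiling, because the section itself expects much less TB in HIV- prisoners.

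**Sampling error for scale.** At an assumed sensitivity of 0.80, the 95% half-width is 1.96 × √(0.8 × 0.2 / cases). This is 16 points with 25 cases, 13 with 38, 11 with 50 and 9 with 75.

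**Size of the selection bias.** The documents give no figure, so it was simulated. Assumptions: normally distributed scores in cases and non-cases, true AUC 0.7-0.9, equally good strategies with correlation 0.5, and the cut-off chosen by maximum Youden index unless stated. Optimism is the apparent minus the true sensitivity, in percentage points.

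| What is chosen on the same data | 25-38 cases | 50-75 cases |
|---|---|---|
| One strategy, 5 cut-offs (AUC 0.7-0.8) | 2.8 to 5.1 | 1.6 to 2.3 (75 cases only) |
| One strategy, 27 thresholds | 3.2 to 6.6 | 1.8 to 4.1 |
| Best of 5-10 strategies, 27 thresholds | 8.0 to 15.3 | 5.4 to 10.6 |
| One strategy, specificity floor of 70% | -0.3 to 0.4 | -0.2 to 0.4 |
| Best of 5-10 strategies, specificity floor of 70% | 4.6 to 10.6 | 2.9 to 6.9 |
| Strategy and cut-off fixed in advance | 0 | 0 |

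Under the Youden rule, specificity is overstated by under 1 point for one strategy and by at most 2 points for the best of 5-10.

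**A setting nearer the plan's own example.** Take five symptoms, present in 20-45% of cases and 12-30% of non-cases, with or without Xpert (positive if either is positive). Assume Xpert sensitivity 0.5-0.8, specificity 0.98 and conditional independence. Choosing the best of 5 symptom-count cut-offs overstates sensitivity by about 1-4 points with 25-38 cases and about 0.6-3 points with 50-75. With the first row of the table, this gives the 1-5 point range for one strategy with 25-38 cases.

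**The AIC step.** Three covariates with assumed pairwise correlation 0.8 were simulated, with AIC choosing one, and compared with a fixed covariate. Sensitivity optimism rises from 8.5 to 9.3 points at n = 250 and from 4.7 to 5.0 at n = 500. The AIC choice therefore adds under 1 point, and AUC optimism rises by only 0.004-0.005.

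**The case against.** The strongest defence is that the plan says thresholds will be examined, not that the best one will be chosen and reported alone. A full table or ROC curve creates no selection bias. For one strategy with few cut-offs, the bias is also small beside the sampling error. Both points stand, and the concern is conditional for that reason. They do not remove it: Section IX expects Part A to name a best strategy, and nothing in Section V.12 limits how many combinations or cut-offs compete for that place.

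Four stronger readings are tempting, and the documents do not support them.

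- A reader might infer that AIC picks the screening strategy, or imagine a wide stepwise search over many predictors. The AIC sentence covers age, duration of drug use and duration of smoking only, and no such search is described.
- A reader might infer that the overstatement is certain. It depends on a choice the plan leaves open. It is zero with fixed cut-offs and near zero with a specificity floor and one strategy.
- A reader might infer that the planned 95% intervals are invalid. The accuracy intervals stated are for Xpert against culture, where nothing is tuned. For combinations no interval method is given.
- A reader might infer that an inflated sensitivity is a stated input to Aim 2. The text mentions the precision of the estimates and the use of Aim 1 data. Carry-over of a tuned sensitivity is plausible but not stated.

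**Conclusion.** The concern holds in conditional form. Part A leaves strategies and cut-offs open, has few cases and plans no internal validation. If the best rule is chosen and reported on the same participants, its sensitivity will tend to be overstated by about 1-5 points with 25-38 cases (one strategy, five cut-offs). The excess is roughly 5-15 points, across 25-75 cases, if the best of 5-10 strategies over many thresholds is also picked.

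The direction is secure. The size is less so, because the AUC, the number of strategies, their correlation, the symptom frequencies, the Xpert accuracy and the selection rule are all assumed. The point affects Part A's comparison of strategies, and Aim 2 so far as these estimates are used there. It does not affect the Xpert-alone results or invalidate the study.

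**What to change.** Amend Section V.12, Part A, as follows.

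1. List in advance the strategies to be compared and the cut-off for each. Rules fixed this way, such as any WHO symptom, smear alone or Xpert alone, need no correction.
2. For any combination or cut-off still chosen from the data, state the selection rule. Repeat the whole selection, including the AIC choice where used, in at least 500 bootstrap samples.
3. Report optimism-corrected sensitivity, specificity and AUC with bootstrap intervals, beside the fixed rules.
4. Use the corrected values, with their uncertainty, wherever these estimates enter Aim 2.

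The cost is some analyst time and a few sentences in the plan, with no new participants or data. The downside is that combined strategies will look slightly less favourable.

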in a 12HR combination since both isoniazid and rifapentine can damage the liver; CDC is calling for studies of 12HR in prisoners, but have not yet funded research. In the absence of studies of 12HR use in prisoners, it is crucial to assess both completion rates and tolerability (especially when high HCV prevalence is present).

Eligibility for Part B includes:

- 1) Meets inclusion criteria for Part A
- 2) Has latent TB (HIV+, or TST \geq 10mm (HIV-)) and no active TB disease
- 3) \geq 6 months before end of sentence to ensure option for treatment completion
- 4) AST/ALT <5 ULN, or AST/ALT <3 x ULN if TBil >2 x ULN
- 5) Not on a protease inhibitor (drug interaction with rifapentine)
- 6) No known porphyria
- 7) Not pregnant (women only).

Enrolled participants will undergo block stratified randomization, stratifying on four factors: a) CD4 <350 (if HIV+); b) HCV Ab status; c) ART status; and d) opioid dependence. After randomization and allocation to 12HR or 26H, participants will be provided 12HR weekly (12 weeks) and 26H daily (26 weeks) as directly observed therapy. Every 4 weeks, patients will be monitored for AST/ALT, adverse side effects and pregnancy. Premature treatment discontinuation will occur for any DAIDS Grade 4 toxicity, patient refusal to continue, or pregnancy (women only).

Study Design: TB Studies

Legend: LTBI=latent TB infection; H=isoniazid; HP=isoniazid + rifapentine; MMT= methadone maintenance treatment; BPN/NLX= buprenorphine/naloxone; OAT=opioid agonist treatment; ART= antiretroviral therapy; HCV= hepatitis C virus.

Part C:

A two-arm **preference trial** (no MAT, and methadone) of prisoners with opioid use disorders who are not or are currently being treated for TB and/or HIV, and are about to transition to the community and need to continue their treatment post-release. Patients may or may not be returning to Klang Valley and within 25 km of our research site. We anticipate enrolling 25-50 participants per arm.

Once consented, study participants will be provided an informed decision-making aid that will help them decide if medication-assisted treatment, specifically Methadone, is best for them. Participants will also have the option not to enroll in medication-assisted treatment.

[figure not shown]
Informed decision-making aid:

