- 1) Selecting experts in the field (HIV, TB, Substance abuse) who will serve as members of the board. If funded, we will select two U.S. and one Malaysian experts to serve on the DSMB. As in other NIDA trials, we will work with NIDA staff to select these individuals. Individuals from NIDA will be responsible for the final invitation to participate on the Board. During the first six months of the study, while final implementation is being conducted, the DSMB will convene to go over their charge, examine the guidance set forth by the study team and to question the PI and biostatisticians about pre-defined endpoints. Once these outcomes and stopping rules are defined, the Board will reconvene at regularly scheduled times to assess outcomes.

Defining stopping rules. For Aim 1, part B, we will be examining completion and tolerability of two LTBI prevention strategies. The study is not powered to reduce development of active TB, but to establish safety in prisoners who have high prevalence of HCV infection. Tolerability (discontinuation from study medication) will be the primary outcome. All discontinuations will be reviewed by the PI and the team. Death will be brought to the DSMB within 24 hours if medication related (though most deaths are related to TB itself). If the discontinuation rate is 3-fold higher in either group, either in the interim analysis when 50% is enrolled or at any time within study assessment, the study will be stopped for safety purposes and a press release will be made. For Part B, we anticipate a difference between the control group and the two intervention groups of about 40%.

- 2)
- 3) Assessment of possible adverse consequences of the various interventions. No specific guidance is available for DSMBs for these kinds of interventions; however, we have considerable experience with CHRP, Project PLUS, Project TRUST, Project CONNECT, Project BEST and other community research studies to provide a specific plan. In fact, in order to collect information about the "safety" of the intervention, we intend to hire a research assistant to gather safety information from three independent sources. These include the weekly study meeting where all active participants are discussed, daily conversations with the Health Educators and weekly conversations with the subject

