
Part B: In CDC's original non-inferiority trial of 26H v 12HR, treatment completion differed significantly (67.0% v 82.1%); however, there were no HIV+s (and therefore no ART prescribed)

and HCV infection was <3%. Therefore tolerability for a longer exposure to 26H may decrease completion further. We will compare the proportion completing TB preventive therapy (no adverse side effects) for the two groups and control for any confounders that may differ after randomization. Using an alpha=0.05 and power=0.8 and a 20% difference (most conservative), we would need 118 per arm. We hypothesize, however, that 26H will be tolerated even less based on studies of IPT hepatotoxicity in a RCT of isoniazid in prisoners (21% in with HCV)⁴² and HCV+ patients (correlated with longer IPT exposure).⁴³⁻⁴⁵ Thus, even increasing the difference in treatment completion to 20% (still conservative), the sample size would need to be 164. Thus, we will conservatively enroll 177 per arm or 354 patients total. We will analyze the data two ways, including ITT as a difference in proportion of treatment completion used in RCTs. In order to discern factors associated with differences in treatment completion, we will treat the entire recruited sample as a cohort and using Cox regression, examine time to treatment discontinuation between the two groups using Cox Proportion Hazards as well as examine the independent factors associated with treatment discontinuation (e.g., being on ART, HCV status, baseline AST/ALT, CD4 strata, etc).

Part C: Eligibility will be having no TB disease, TB disease or LTBI, on TB medications that must be completed after release, and meet pre-incarceration DSM-V criteria for opioid dependence. We will compare a control group of prisoners choosing no OAT and compare them to OAT patients. Even though we anticipate 15-20% attrition, we will count missing=failure to be conservative and will censor the data based on the mid-point between the last and the missed visit. The primary outcome will be the proportion completing treatment for active or LTBI. Secondary analyses will compare Kaplan Meier curves using Cox proportion hazards and time to discontinuation. TB treatment adherence will also be measured using MEMS caps and analyzed as we have done previously in TB patients in Ukraine.

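### Part B stratifies randomisation on four factors but does not prespecify them in the completion comparison; naming them is a small improvement that needs no new data

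*Combined protocol and SAP*

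**What the plan says.** Section V.3, Part B: "Enrolled participants will undergo block stratified randomization, stratifying on four factors", namely "a) CD4 <350 (if HIV+); b) HCV Ab status; c) ART status; and d) opioid dependence". Block size is not given.

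Section V.12, Part B, describes three analyses:
- The proportions completing preventive therapy are compared, and the analysts will "control for any confounders that may differ after randomization". No covariate, model, test or threshold is named.
- The data are analysed by "ITT as a difference in proportion of treatment completion used in RCTs", with no covariates mentioned.
- A Cox analysis of time to discontinuation compares the arms and looks for "independent factors associated with treatment discontinuation (e.g., being on ART, HCV status, baseline AST/ALT, CD4 strata, etc". Three of the four stratification factors appear there as examples. Opioid dependence does not, and the text does not say which covariates enter the treatment comparison.

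The stopping-rule text in Section V.11 adds that "Tolerability (discontinuation from study medication) will be the primary outcome". How that fits with completion in Section V.12 is a separate matter, but it is a reason to treat both analyses alike in the fix.

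**The concern.** Factors used to stratify randomisation are usually chosen because they are expected to predict outcome, and the analysis should then reflect them. Here the only adjustment of the completion comparison is triggered by observed imbalance. Stratified blocks are meant to prevent imbalance in exactly these four factors, so the trigger works against the design. HCV is the clearest case: Section V.12 cites isoniazid hepatotoxicity in HCV-positive prisoners as a reason to expect worse tolerability of 26H, yet the clause would almost never bring HCV into the model.

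Two things are at stake, both modest. If the factors are prognostic, the unadjusted standard error ignores precision that the design has already secured, so the interval is a little too wide and some power is lost. The adjusted estimate also cannot be specified in advance, because it depends on which variables are judged to differ.

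**Working it through.** **Inputs from the documents.** 177 per arm, 354 in total; alpha 0.05 (taken as two-sided); completion 82.1% on 12HR, and 67.0% (Section V.12) or 69.0% (Section V.3) on 26H; planning difference 20 points; HCV antibody 94% in HIV+ and 63% in HIV-. The HIV+ share of Part B is not stated. It is varied from 5% (intake prevalence) to 50% (the 250/250 sample of Part A).

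**Assumptions.** CD4 <350 and ART each in 50% of HIV+; opioid dependence 60%; the same odds ratio (OR) for non-completion for each factor (1.0, 1.65 or 2.7); blocks of 4, 10 or 20; 1:1 allocation; 'differ' read as p<0.05.

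**The plan's own sample size.** The plan gives 118 per arm for a 20-point difference at 80% power. The most demanding base rate is 40% v 60%: (1.96×√0.5 + 0.842×√0.48)²/0.2² = 97 per arm (107 with continuity correction). So 118 does not follow from its stated inputs. That is a separate point; the working below uses the enrolled 177 per arm.

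**Unadjusted power at 177 per arm.** Power = Φ{[Δ√n − 1.96√(2p̄(1−p̄))] / √(p₀(1−p₀)+p₁(1−p₁))}, with √177 = 13.304.
- 69.0% v 82.1%: (1.743 − 1.191)/0.601 = 0.918, giving 82.1%.
- 67.0% v 82.1%: (2.009 − 1.207)/0.607 = 1.321, giving 90.7%.
- 62.1% v 82.1% (82.1% minus 20 points; base rate assumed): (2.661 − 1.243)/0.618 = 2.29, giving 98.9%.

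**How often the clause would select a stratification factor.** In 150,000 simulated trials, HCV or opioid dependence was flagged in none. CD4 or ART was flagged in 1.1-1.3% of trials (blocks of 4) to 6.2-6.6% (blocks of 20) at 5% HIV+, and in about 0% at 50% HIV+.

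**Power gained by prespecified adjustment over the imbalance rule, in points** (10,000 trials per design cell, 16 strata; linear risk-difference model, main effects, robust standard errors):

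| 26H v 12HR completion | OR per factor | 5% HIV+ | 50% HIV+ |
|---|---|---|---|
| 67.0% v 82.1% | 1.65 | 0.2-0.6 | 0.6-0.8 |
| 69.0% v 82.1% | 1.65 | 0.4-0.8 | 1.3-1.5 |
| 67.0% v 82.1% | 2.7 | 1.2-1.3 | 2.1-2.7 |
| 69.0% v 82.1% | 2.7 | 2.1-2.4 | 3.9-4.0 |

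At OR 1.0 the change is -0.3 to +0.2 points. At 62.1% v 82.1% it is under half a point either way, even at OR 2.7.

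**Interval width.** The ratio of unadjusted to adjusted width is about 1/√(1−R²). At OR 1.65 the simulated R² was 0.043 (20% HIV+) to 0.054 (50% HIV+), giving 1.022 to 1.028. Direct simulation gave 0.7-2.1% wider. Together that is roughly 1-3%. At OR 1.0 the unadjusted interval is 0.3-0.8% narrower.

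**Type I error, imbalance rule v prespecified model.** OR 1.65: 4.1-5.0% v 4.7-5.4%. OR 2.7: 3.1-4.3% v 4.6-5.3%. The error is on the conservative side.

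**The case against.** The strongest reply is that almost nothing is lost. At the plan's own 20-point difference, power is about 99% with or without adjustment. At 13-15 points, power under the imbalance rule stays at 81.7-92.8% in every scenario run. The larger gains need OR 2.7 on all four factors, which implies 26H completion falling from 89-94% with no factor to 13-24% with all four; the documents do not support that. The p<0.05 trigger is an assumption, since the plan names no test. The plan also fixes an unadjusted intention-to-treat difference in advance, and its Cox analysis mentions three of the four factors. If the factors predict nothing, adjustment costs a fraction of a point. All of this stands, and it is why the point is minor. It does not supply the missing covariate list.

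Three stronger readings are tempting and should be resisted.
- A reader might infer that the completion test is invalid or inflates false positives. It does not: the unadjusted difference is valid, and it errs towards caution after stratified randomisation.
- A reader might infer that the trial is underpowered for want of adjustment. The figures above show otherwise.
- A reader might infer that covariates will be chosen with outcomes in view, because "All discontinuations will be reviewed by the PI and the team". That sentence belongs to the safety-monitoring plan. It does not describe a comparison by arm or any role in choosing covariates. A simulated free choice among adjustment sets raised alpha to about 0.07, but nothing in the documents says that such a choice will be made.

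**Conclusion.** The point holds as a minor one. The four randomisation factors are not prespecified in the completion comparison, and the clause that governs adjustment is one that stratification all but prevents from selecting HCV or opioid dependence.

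The gain in power from naming them is about zero at the 20-point planning difference or if the factors are not prognostic, about 0.2-1.5 points at 13-15 point differences with OR 1.65 per factor, and about 4 points only in the extreme OR 2.7 case. At OR 1.65 the unadjusted interval is roughly 1-3% wider than the adjusted one. These sizes depend on assumed odds ratios, prevalences and block sizes. The gap in the wording does not. The other benefit, an adjusted estimate fixed in advance, needs no assumption about prognosis.

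**What to change.** Before outcomes by arm are examined, including at the interim look at 50% enrolment in Section V.11, delete the clause on confounders in Section V.12, Part B, and put one prespecified analysis in its place:

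- The intention-to-treat risk difference in completion, from a linear (or standardised) risk-difference model with robust standard errors. This keeps the plan's difference in proportions as the estimand; a logistic odds ratio would change it.
- Main effects for the four factors as coded at randomisation, plus an HIV indicator so that CD4 and ART are defined for HIV- participants. Full cell-by-cell adjustment is not advised: the factors form 16 cells, or up to 20 if HIV is kept separate. At 5% HIV+ only about 18 participants (0.05 × 354 = 17.7) would be HIV+.
- The unadjusted difference reported alongside.
- The same factors in the Cox treatment comparison, with any further covariate search labelled exploratory.

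If outcomes by arm have already been examined, keep the unadjusted difference as the main result and label the adjusted one supportive.

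The cost is a few sentences in the analysis plan, dated. No data are added for the four factors, which must be known in order to randomise, and HIV status comes from the mandatory intake test.
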